## **7.0 Risks**

### ***a. Risks to human subjects***

1. Redness, swelling, burning, rash, or discomfort may occur at the site of the lanadelumab injection. Should this occur we will put ice on the site.
2. Lanadelumab may increase the risk of upper respiratory infections. Cold symptoms such as runny nose, sore throat, and sneezing are commonly observed. We will closely monitor the occurrence of those symptoms, and if necessary, we will stop the study.
3. Other side effects of lanadelumab include headache, muscle pain, and diarrhea. These side effects are uncommon but will be monitored during the study. If any of them persist, the patient will be withdrawn from the study.
4. Lanadelumab may induce elevation of transaminases, which is rare and transient. We will closely monitor the transaminase levels, particularly after the administration of the study drugs.
5. Lanadelumab may pose unforeseeable risks to the subject, an embryo or fetus, or a pregnant woman. Pregnant women are excluded.
6. Should new information become available during the study that may influence a subject's willingness to participate, we will make that information available and amend the consent form appropriately.
7. The collection and storage of DNA for genotyping creates the risk of release of information that could link subjects to stored samples and genotyping results.

## **8.0 Reporting of Adverse Events or Unanticipated Problems involving Risk to Participants or Others**

### **Protection against risk**

- Investigators will obtain a detailed medical history to look for the exclusion and inclusion criteria. Patients will also undergo a complete physical examination prior to being included in the study. The assessment will include a thoughtful evaluation of the cardiovascular system, including blood pressure.
- Patients will be monitored for the presence of Type I hypersensitivity reaction after the administration of the first study drug. For this purpose, the patient will remain in the CRC for two hours after the administration of the study. If the patient presents this type of reaction, proper treatment will be administered in the CRC. Also, the patient will not receive the second dose of the study drug and will be withdrawn from the study.
- Baseline laboratory analysis and metabolic panels will be obtained to screen for any hematological or biochemistry abnormality.
- A resting electrocardiogram (ECG) will be obtained during the CRC visits to look for the presence of abnormal ST segments, T-wave inversion, or cardiac arrhythmias.
- Diagnosis of myocardial infarction will require the presence of at least two of the following criteria: typical chest pain with or without radiation, electrocardiogram compatible with myocardial infarction, and elevation of cardiac enzymes (creatinine kinase MB or troponin). Stroke will be defined as new and sudden onset of neurological deficits that lasts longer than 24 hours.
- We will review blood pressures obtained at the dialysis center. If at any time the pre-dialysis systolic blood pressure exceeds 189 mmHg or diastolic blood pressure exceeds 114 mmHg, blood pressure will be closely monitored. In the case of uncontrolled high blood pressure, subjects will be discontinued from the study.
- A serum **pregnancy test** will be obtained the day of the study drug administration in all women with childbearing potential to exclude pregnancy.
- Serum electrolytes will be measured before study visits in blood draws for clinical labs (See Appendix A). Also, we will monitor potassium levels using the monthly labs obtained in the hemodialysis unit. For serum potassium from 5.5-5.9 mmol/L, the dietary restriction will be emphasized, and the potassium content of the dialysate will be adjusted to decrease serum potassium. Predialysis serum potassium of 6.0-6.4 mmol/L, if confirmed and not corrected with adjustment of dialysate potassium concentration, will result in discontinuation of the study. Confirmed predialysis serum potassium of 6.5 mmol/L or greater will result in immediate discontinuation. All potassium measurements will be obtained before dialysis.
- Transaminases levels will be monitor after the administration of the first study drug. If the levels increase four times the upper limit of normal the patient will be excluded from the study and will not receive the second dose of the study drug.

Also, if the levels of the transaminases do not return to normal within one week after the elevation, the patient will not receive the second dose and will be excluded from the study.

- There are many safeguards in place to prevent the release of information from this study. All research samples are coded with the subject's unique identifier. Data sets used for the analysis also only contain this identifier. The key to the code is protected. Only the investigator, co-investigators, and research nurse have access to information that identifies subjects as participating in the study. The results of tests run on research samples will not be recorded in any subject's medical record, and neither the subject nor his or her doctor will be told of the results, except in the case of unsuspected significant arrhythmia or myocardial infarction. Access to the Vanderbilt computer network is protected at the level of firewalls, TCP wrappers, and University assigned user IDs. Data are secured with encryption algorithms, and the network is maintained by the Medical Center's Network Computer Service.

### **Data and Safety Monitoring Plan**

The principal investigator will be responsible for ensuring the data integrity and safety of all the study participants. All the adverse events will be recorded and reported to the Vanderbilt University Medical Center Institutional Review Board (IRB). The study progress report will be prepared every 6 months to describe: the screening and recruitment process, demographic of the participants, status and occurrence of adverse events (AEs), drug toxicities, treatment adherence, and any incident of non-compliance with the protocol. These reports will be prepared by the principal investigator. The reports will be presented to the Data and Safety Monitor (DSM) committee. The DSM may choose to perform an interim analysis; however, it is expected that this would not occur without reasonable concern related to either patient safety or data validity. The DSM may choose to become unblinded; however, it is expected that such unblinding would not occur without reasonable concern related to either patient safety or data validity.

Protocol changes will be reported to the IRB and will not be implemented until approval is obtained.

The DSM will objectively review the treatment results as they relate to human safety and data quality. Drs. [name], [name], [name], and [name] have agreed to be members of the DSM committee. [name], Professor of Medicine and Pharmacology and Director of the Vanderbilt Autonomic Dysfunction Center, with extensive experience in human research and clinical trials, has agreed to take the role of DSM committee chair. [name] is Associate Professor in the Division of Nephrology who focuses on patient education and awareness regarding chronic kidney disease. [name] is Assistant Professor in the Division of Clinical Pharmacology with background in epidemiology and bioinformatics. [name] is a biostatistician with extensive experience as a consultant with the Department of Medicine. None of the members of the DSM committee have any conflict of interest, whether financial or intellectual with the investigator or the sponsor of the study.

All protocols have been or will be reviewed and approved by the Vanderbilt University Medical Center IRB before any subject is enrolled.

The principal investigator and co-investigators will closely oversee the protocol in

conjunction with the dedicated research nurse. Any AEs or toxicities will be reported to the IRB as per IRB guidelines. Any untoward medical event will be classified as an AE, regardless of its causal relationship with the study. An adverse event will be classified as serious if it a) results in death, b) is life-threatening, c) requires inpatient hospitalization or prolongation of existing hospitalization, d) results in persistent or significant disability or incapacity, or e) is a congenital anomaly or birth defect. Serious adverse events will be reported to the DSM, the IRB, the National Institutes of Health (NIH), and the FDA within 7 days of the PI's notification of the event. Non-serious, unexpected adverse events and instances of non-compliance with the protocol will be reported to the DSM and IRB at the time of continuing review.

## **9.0 Study Withdrawal/Discontinuation**

Subjects who develop an adverse event that is not transient (such as persistent nausea, diarrhea, headache, etc.) will have any study drug discontinued and will be withdrawn from the study. Subjects who do not tolerate the first dose of lanadelumab will be withdrawn from the study. Subjects who are withdrawn will be treated and/or followed as appropriate until any symptoms are resolved. If in the opinion of the investigator a subject is non-compliant, the subject will be withdrawn from the study. Subjects may withdraw from the study at any time.

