## **5.0 Enrollment/Randomization**

This is a parallel study where participants will be assigned to either taking the study drug (lanadelumab) or taking the placebo (saline pre-filled syringes.) Patients will be randomly assigned to the treatment order using a permuted-block randomization algorithm. The study drug, lanadelumab, will be shipped from Takeda as pre-filled syringes along with matching placebo, also in prefilled syringes. The Vanderbilt Investigational Drug Services (IDS) will be responsible for the storage, preparation, dispensing, and labeling of the investigational agents. The Vanderbilt IDS will also maintain accurate drug storage and dispensing logs. Subjects will be randomized to receive a placebo or 300 mg of lanadelumab (Takeda Pharmaceutical, Cambridge, MA). Subjects randomized who do

not complete the whole protocol for any reason will be replaced, and their data will be analyzed separately. The half-life of lanadelumab is 14 days, and the time to reach maximum concentration is five days. For this reason, we will monitor blood pressure and the occurrence of DIH for three weeks after the administration of the second dose of the study drug.

[figure not shown]

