## 6.0 Study Procedures

### Study protocol

After obtaining consent, study subjects will undergo the following procedures.

**COVID-19 precautions prior to and during visits.** Pre-visit phone call – we will contact the patient before all of their study visits to ask a series of COVID-19-related screening questions. Depending on their answers, we will continue with the study visit or postpone for another time. The patient will be asked to wear a face covering during all portions of their study visits in which they are in the presence of hospital staff. We will also encourage frequent hand washing and/or provide alcohol-based hand sanitizer.

Subjects will participate in a randomized, parallel-group, double-blind, placebo-controlled study in which they will receive two doses of placebo or 300 mg of lanadelumab subcutaneously. Participants will continue their usual medications throughout the study. One week (Day -7) before the administration of the first dose of the study drug, we will conduct a study visit at the hemodialysis unit. During this visit, we will give the participants a physical activity monitor to be worn for at least 5 consecutive days and will obtain baseline blood samples. During a second study visit at the dialysis unit (Day -1), we would obtain a second baseline blood sample one to three days before the administration of the first dose of the study drug. In this visit, we will also measure

muscle oxygenation using near-infrared spectroscopy (NIRS). Patients will be then asked to come to the Vanderbilt Clinical Research Center (CRC) on a non-dialysis day. During this visit (Day 0), we will obtain a detailed history, perform a physical examination, administer a quality of life (QOL) questionnaire, obtain the dialysis recovery time, and evaluate body composition and physical performance. We will then administer the first dose of the study drug and monitor the appearance of any Type I (immediate) hypersensitivity reaction for two hours before discharging patients from the CRC. We will repeat the same protocol, as outlined for Day 0 and administer the second dose of the study drug two weeks later at the CRC (Day 14).

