The next two consecutive dialysis treatments after each drug administration (days 1 and 3, and days 15 and 17), we will conduct follow-up visits at the dialysis unit to collect information regarding symptoms after discharge from the CRC. During these visits, at the end of every hemodialysis session, we will also inquire, through a standardized questionnaire, about the presence of any symptoms associated with hypotension. This questionnaire will include symptoms such as cramps, dizziness, nausea, and will be scored according to the severity from 0 to 4 (none to severe). We will also collect blood samples at the dialysis unit for pharmacokinetics and special laboratory analysis. During the six-week length of the study, we will monitor the occurrence of DIH episodes and changes in blood pressure in every dialysis session. For this purpose, we will use the dialysis clinic blood pressure monitor logs. We will also conduct two additional visits at the dialysis units (Day 29 and 43) to draw blood, administer the symptomatology questionnaire, and measure blood flow with NIRS. In the final hemodialysis visit (day 43) we will also give the patients an activity monitor that will be collected after five consecutive days of continuous use. During this last visit, we will also administer the QOL questionnaire, obtain the dialysis recovery time, and perform body composition and physical performance tests (except for the six-minute walk test). Details of the study protocol can be found in Figure 5, Tables 1 and 2, and Appendix 1

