### **Dialysis Recovery Time**

We will ask the patients "How long does it take to recover from a hemodialysis session", as described in a previous study. This information will be collected during the follow-up phone call or the visit at the next regular hemodialysis session. The answer will be recorded in minutes. We will convert the following answers to numbers: 1. One day = 1440 minutes; 2. More than one day = 2160 minutes, or 3. Half-day or next day = 720 minutes

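### Safety exits end study participation rather than only dosing, no off-drug outcome follow-up is planned, and those patients are then replaced and analyzed apart

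*Combined protocol and SAP*

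**What the plan says.** Section 9.0 states that a patient with a non-transient adverse event "will have any study drug discontinued and will be withdrawn from the study", and it also withdraws anyone who does not tolerate the first dose. The same consequence appears elsewhere:

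- Section 7.0, for listed side effects such as headache, muscle pain and diarrhea: "If any of them persist, the patient will be withdrawn from the study".
- Section 8.0, Protection against risk: hypersensitivity (no second dose, and withdrawal), uncontrolled high blood pressure (discontinued from the study) and transaminase elevation (no second dose, and exclusion).
- The potassium rules in Section 8.0 are unclear. The 6.0 to 6.4 mmol/L rule speaks of discontinuing the study. The rule for 6.5 mmol/L or more speaks only of immediate discontinuation.

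On what happens next, Section 9.0 says: "Subjects who are withdrawn will be treated and/or followed as appropriate until any symptoms are resolved". It does not mention collecting outcomes or reading clinic logs after exit. Section 5.0 says that randomized patients who do "not complete the whole protocol for any reason will be replaced, and their data will be analyzed separately". Section 10.0 b repeats the replacement rule and names no other way of handling missing data.

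Doses are given on Days 0 and 14 only. Section 5.0 uses the 14-day half-life and the five-day time to peak to justify longer observation: "we will monitor blood pressure and the occurrence of DIH for three weeks after the administration of the second dose of the study drug". Section 6.0 and Appendix A extend session monitoring and visits to Day 43.

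**The concern.** Stopping a drug and leaving a trial are different events, and the plan joins them. Two kinds of patient are affected.

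1. A patient who stops after the first dose may have no data in the primary window, because nothing requires that blood pressure still be collected.
2. A patient who meets a limit after Day 14 has already received both doses. Exit reduces no exposure, but it ends scheduled monitoring. The replacement rule then sets this patient aside even if the primary outcome was already recorded.

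Some triggers overlap with what the trial measures. Persistent nausea is an exit trigger and a scored symptom, and uncontrolled blood pressure is an exit trigger in a blood pressure trial. Headache, muscle pain and diarrhea are listed drug effects. Loss could therefore differ between arms and relate to outcome. The main comparison would then be among patients who tolerated the regimen, not among those randomized.

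The withdrawal rules and the replacement rule act separately. Changing only Section 5.0 keeps data already collected but leaves early leavers without window data. Changing only Sections 7.0 to 9.0 collects the data but still analyzes them apart.

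**Working it through.** **Inputs.** Section 10.0 a: 16 per arm, difference 13.7 mmHg, SD 13.6 mmHg, two-sided 0.05, 80% power. Section 10.0 b: drop-out of 10% or less. Dosing on Days 0 and 14, last visit Day 43, thrice-weekly dialysis. Assumed: how far leavers differ from completers, and how much effect one dose has.

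**The plan's own figure.** For two independent means, n = 2 × (1.960 + 0.842)² × (13.6/13.7)² = 15.5, so 16 per arm. The figure reproduces on this basis. The two-sample t-test gives 78.7% power at 16 per arm, which is the baseline used below. (The paired test named in the plan is a separate matter.)

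**How many patients.** 10% of 32 = 3.2, so about 3 from all causes. The safety rules account for only part of that.

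**Monitoring lost, at nominal days.** Any 7 consecutive days hold 3 sessions.

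- Exit after Day 15: Days 16–43 are 28 days, so 12 sessions.
- Exit after Day 29: Days 30–43 are 14 days, so 6 sessions. The three weeks promised in Section 5.0 end on Day 35. Days 30–35 hold only 2 or 3 of those 6; the rest belong to the monitoring in Section 6.0 and Appendix A.

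**Primary-window data.** The window is three sessions in the second treatment week. All 3 are lost if the patient leaves by Day 7 and the window is Days 8–14 (the plain reading). If the window were counted after dose 2, all 3 are lost on exit by Day 14 (Days 15–21) or by Day 21 (Days 22–28). Visit windows in Appendix A can move these days.

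**Possible shift from setting leavers aside.** With 16 completers and k leavers in one arm, who differ by d on average, shift = k/(16 + k) × d. Take d = 0.5 to 1 SD = 6.8 to 13.6 mmHg.

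- k = 1: 1/17 × 6.8 to 13.6 = 0.4 to 0.8 mmHg.
- k = 3: 3/19 × 6.8 to 13.6 = 1.1 to 2.1 mmHg, or 8% to 16% of 13.7.
- The standard error of the two-arm difference is 13.6 × √(2/16) = 4.8 mmHg, so k = 3 is 0.22 to 0.45 standard errors.

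This is an illustration, not a bound.

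**Price of keeping them in.** Suppose the window follows dose 2 and all k one-dose patients are on lanadelumab. If a share f of the effect remains after one dose, dilution = 13.7 × k(1 − f)/(16 + k). Power is for the two-sample t-test with SD 13.6.

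| Case | Dilution (mmHg) | Effect (mmHg) | Power |
|---|---|---|---|
| None | 0 | 13.7 | 78.7% |
| k = 1, f = 0, replaced (17 vs 16) | 0.8 | 12.9 | about 75% |
| k = 3, f = 0, replaced (19 vs 16) | 2.2 | 11.5 | about 68% |
| k = 3, f = 0, not replaced (16 vs 16) | 13.7 × 3/16 = 2.6 | 11.1 | about 61% |

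With f = 0.5, dilution with replacement is 0.4 (k = 1) to 1.1 mmHg (k = 3). If the window is Days 8–14 it is nil, because dose 2 comes on Day 14 and cannot affect those sessions.

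**The case against.** The strongest reply is that the effect is small and the remedy has a price of similar size. The shift needs every leaver in one arm and a difference of 0.5 to 1 SD, and it still stays under half a standard error. Dilution from keeping one-dose patients (0.8 to 2.2 mmHg with replacement) is about as large. On the plain reading of the window, a patient loses all primary data only by leaving within the first week. All of this stands, and it limits the point to a modest one.

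The two costs are not alike, however. Dilution reflects what assignment to the regimen achieves, and it can be estimated from collected data. A shift from patients who were never measured or were set aside cannot be seen at all.

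Three stronger readings are tempting, and the documents do not support them:

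- *That the plan states these patients are excluded from the main analysis.* It says only that they are analyzed separately, and it defines no main analysis set. Exclusion is the likely meaning once they are replaced, but it is an inference.
- *That loss will differ by arm.* The overlap of triggers with outcomes and listed drug effects makes this plausible. Nothing in the plan shows it.
- *That safety follow-up stops at exit.* Section 9.0 follows symptoms to resolution, and Section 8.0 records all adverse events. What is missing is outcome follow-up, and any stated laboratory follow-up when an abnormality causes no symptoms.

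**Conclusion.** The point holds and should be corrected, at modest size. As written, meeting a safety limit removes a randomized patient from the study, no outcome data are planned afterwards, and the patient is replaced and most likely left out of the main comparison. The clearest fault lies after Day 14: no exposure is avoided, yet up to 12 sessions of monitoring are given up (6 after Day 29), and primary data already in hand can be set aside. That part needs no assumption about bias, only the nominal schedule.

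The effect on the primary result is conditional: about 0.4 to 2.1 mmHg of 13.7 for 1 to 3 leavers, all in one arm and differing by an assumed 0.5 to 1 SD. It is zero if loss is balanced or unrelated to blood pressure. A reader might infer that the primary result is materially biased; the documents do not support that.

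**What to change.** Keep every clinical limit, and change what follows from meeting one.

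1. **Sections 7.0, 8.0 and 9.0.** State that meeting a limit withholds any dose still due, while the patient, with consent, stays in light follow-up to Day 43. This covers clinic-log blood pressure and DIH, adverse events, safety laboratories, symptoms and recovery time. Arterial and venous research sampling and CRC tests may be dropped.
2. **Section 8.0, potassium.** State whether each threshold stops the drug or the patient's participation.
3. **Sections 5.0 and 10.0 b.** State that every randomized patient who received a dose is analyzed in the randomized arm with all available data. This applies whether the patient stopped dosing, met a limit after dose 2, or missed later procedures. Wording limited to patients who stop dosing would miss the second group. Any replacements are added to these patients and do not take their place. Keep the completer analysis as supportive.

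The operational cost is low. Session blood pressure and DIH already come from routine records ("For this purpose, we will use the dialysis clinic blood pressure monitor logs"), and recovery time has an easy route ("This information will be collected during the follow-up phone call or the visit at the next regular hemodialysis session"). The rest is protocol wording and a few patients in light follow-up.

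The statistical cost should be stated in the amendment. If the window follows dose 2, one dose has no effect and all one-dose patients are on lanadelumab, power falls from 78.7% to about 75% (1 patient) or 68% (3 patients) with replacement, and to about 61% for 3 without. If the window is Days 8–14, there is no dilution.
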